All research activities will be performed after obtaining Institutional Review Board Approval from Emory University. A consecutive sample of women will be recruited from the FPMRS and Menopause patients within The Emory clinics. Subjects are identified after their management plan has been established to include treatment of vulvar and/or vaginal atrophy. Patients will be approached by the principal and/or co-investigators. For women that agree to participate, written informed consent will be obtained. All women who agree to participate in this study must meet inclusion criteria listed in Table 1. Once the exclusion criteria have been applied (Table 2), the qualifying subjects will be enrolled in the study. Once enrolled, each subject will complete the Female Sexual Function Index (FSFI) questionnaire and a symptom severity Likert scale. Finally, they will receive instructions on medication compliance, as well as potential adverse events for the designated medication. If we assume 50% of women offered enrollment in this study will agree and be eligible to participate, we expect to reach our target enrollment in seven to eight months.

Table 1. Inclusion Criteria
Interested in resuming or continuing sexual activity

Table 1. Inclusion Criteria

Greater than 12 months since last menstrual cycle or prior bilateral oophorectomy
40yo or older
Dyspareunia as a vulvovaginal atrophy symptom
Normal mammogram within 12 months prior to entry into the study

Table 2. Exclusion Criteria

History or suspicion of breast carcinoma
History of hormone-dependent tumor
Genital bleeding of unknown cause
Ongoing vaginal infection
History of CVA, MI or heart disease, uncontrolled HTN over 160/100
Serious disease or chronic condition that may prevent completion of study, BMI over 40
Hypercoagulable state, or currently on anticoagulant therapy
Use of any exogenous sex hormone within three months from study entry, or during the study
Pelvic surgery within the last 12 months

Randomization and Allocation Concealment

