To our knowledge, there has been no prior study that reported the prevalence of female sexual dysfunction amongst women using vaginal conjugated estrogens, defined as having an FSFI score of 26.55 or less. With an FSD prevalence of 57%, we determine a 50% reduction in the prevalence to be clinically significant. Setting an alpha of 0.05, and a power of 0.80, and assuming a minimum of 15% dropout rate, the sample size is set to 52 in each group.

Specific Aims

Specific Aim 1: To compare the efficacy of each drug in improving sexual function.

- a. Experimental Design: In this study, participants will be asked to complete the 19-question female sexual function index (FSFI) questionnaire at the beginning of the study period and at 12 weeks. The results will be used to compare the effect of each medication on the various domains of sexual function.

The mean total score in each treatment group at baseline will be compared using Student's t-test. Additionally, the score of the components of desire, arousal, lubrication, orgasm, satisfaction and pain will be similarly compared. Later, the change in these scores between the two treatment groups at 12 weeks will be compared using a paired t-test analysis.

Anticipated Results and Interpretation: We expect to see similar results in this study, showing comparable improvements in vaginal lubrication and dyspareunia, while showing greater improvement for overall sexual health in the ospemifene group.

Potential Pitfalls, Alternative Approaches, and Future Directions: We do not anticipate any challenges with the administration and analysis of this questionnaire.

Specific Aim 2: To compare each drug's impact on VVA symptoms

- a. Experimental Design: Participants will complete a Likert scale of symptom severity at the beginning and at the end of the study. The symptoms listed will include dyspareunia, vaginal dryness, vaginal pain, and vaginal itching. The survey will ask them to rate the severity of each VVA symptom on a scale of 0 to 3, with 0 being none, 1 being mild, 2 being moderate, and 3 being severe. It will also ask them to choose their most bothersome symptom (MBS).

The mean score of the MBS in each treatment group at baseline will be compared using Student's t-test. Later, the change in score of the MBS between the two treatment groups at four weeks and again at 12 weeks will be compared using a paired t-test analysis.

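### The dyspareunia rating has no response for women who have not attempted intercourse, so abstaining can be scored as improvement on Aim 2

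*Combined protocol and SAP*

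**What the plan says.** Patient Groups, Table 1, requires a participant to be "Interested in resuming or continuing sexual activity" and to have "Dyspareunia as a vulvovaginal atrophy symptom". Neither criterion asks for recent activity or a recent attempt.

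Specific Aim 2, Experimental Design, describes the symptom survey: "The symptoms listed will include dyspareunia, vaginal dryness, vaginal pain, and vaginal itching", each rated "on a scale of 0 to 3, with 0 being none, 1 being mild, 2 being moderate, and 3 being severe". The woman also names her most bothersome symptom. The comparison is of "the change in score of the MBS between the two treatment groups at four weeks and again at 12 weeks".

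Specific Aim 1 uses the "19-question female sexual function index (FSFI) questionnaire at the beginning of the study period and at 12 weeks". Total scores are compared, and "the score of the components of desire, arousal, lubrication, orgasm, satisfaction and pain will be similarly compared". Item scoring and the recall period are not given.

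No section asks whether sexual activity took place, at baseline or at 12 weeks, or says how a woman without activity is to be scored on either instrument. The plan expects no difficulties with either one.

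**The concern.** A woman who wants to resume sexual activity may be having none at entry, and a woman who is active at entry may stop during the 12 weeks. Neither has current pain on intercourse to rate, yet the scale as described makes her choose a value from 0 to 3 or leave the item blank. If she chooses 0, the best score is recorded for a woman who may be abstaining because treatment has not relieved her pain.

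At stake is the Aim 2 comparison. Treatment is open-label, and willingness to attempt intercourse may depend on knowing which drug one takes, so abstention could differ by arm. Activity status that was never recorded cannot be reliably reconstructed once the data are in.

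**Working it through.** **1. The plan's own figure.** Sample Size Analysis gives 52 per group. With 57% against 28.5%, two-sided alpha 0.05, power 0.80 and unpooled variance:

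n = (1.960 + 0.842)² × (0.57 × 0.43 + 0.285 × 0.715) / 0.285² = 43.4, rounded up to 44; 44 / 0.85 = 51.8, rounded up to 52.

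The figure reproduces. This point does not concern the sample size.

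**2. One woman.** Let b be her baseline dyspareunia score and t the score she would have given at week 12 had she attempted intercourse. If she abstains and answers 0, the recorded change is 0 − b, the change in her pain is t − b, and the error is −t. With b = t = 3, pain unchanged and severe, the record shows a 3-point improvement. With b = t = 2 it shows 2 points, and with b = t = 1 it shows 1. The error can also run the other way: a woman inactive at entry who answers 0 and later resumes with mild pain is recorded as 1 point worse.

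**3. Where it enters the analysis.** Aim 2 analyses the score of the most bothersome symptom, so the error enters only where that symptom is dyspareunia. Every participant must have dyspareunia, and the Introduction calls it the most common symptom of vulvovaginal atrophy, so the choice is likely to be frequent. The documents do not give the share.

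**4. Unequal abstention.** Among women whose most bothersome symptom is dyspareunia, let m be the mean score that abstaining women would otherwise have given, and d the between-arm difference in the share who abstain and answer 0. The spurious difference is m × d. Both inputs are assumptions.

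| m | d = 0.05 | d = 0.10 | d = 0.20 |
|---|---|---|---|
| 1.0 | 0.05 | 0.10 | 0.20 |
| 1.5 | 0.075 | 0.15 | 0.30 |
| 2.0 | 0.10 | 0.20 | 0.40 |

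Over a whole arm these values are multiplied by the share choosing dyspareunia. If that share were one half (again an assumption), the range would be 0.025 to 0.20.

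**5. Equal abstention.** If the same share a abstains in both arms, and abstainers would have scored like the other women in their arm, a true difference shrinks to (1 − a) of its size: 90%, 80% or 70% at a = 10%, 20% or 30%. The result is dilution and added noise, with no false difference.

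**6. Which women belong in the primary FSFI analysis.** Illustrative assumptions: active women change by +4 (SD 6); a share i is inactive at entry, of whom half resume with +15 (SD 6) and half change by 0 (SD 1). The variance of change over all women is Σw(σ² + μ²) − (Σwμ)². At i = 0.10:

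0.90 × (36 + 16) + 0.05 × (36 + 225) + 0.05 × 1 − 4.35² = 59.90 − 18.92 = 41.0.

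Restricting to women active at baseline gives variance 36 but fewer women, equivalent to 36 / (1 − i) per woman randomised.

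| i | All women | Active at baseline only |
|---|---|---|
| 10% | 41.0 | 36 / 0.90 = 40.0 |
| 20% | 45.7 | 36 / 0.80 = 45.0 |
| 30% | 50.2 | 36 / 0.70 = 51.4 |

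Restriction gains almost nothing in precision and loses a little at 30%.

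**The case against.** The survey form is not reproduced, so the absence of a not-attempted option is inferred from a short description. No recall window is stated, and a woman avoiding intercourse because it hurts may rate it severe from memory or leave the item blank. A baseline 0 would sit oddly with the requirement to have dyspareunia. Loss or return of a partner is balanced in expectation by randomisation. If one drug relieves pain better and more women resume, that is a treatment effect on sexual function, which is the primary aim.

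Much of this stands. It means that abstaining *can* be scored as improvement, not that it always will be, and that bias needs abstention to differ by arm. It does not remove the gap: a 0, a remembered rating and a blank are all possible, they mean different things, and no rule covers any of them.

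A reader might go further and infer that an inactive woman scores zero on most FSFI domains, falls at or below 26.55 whatever her function, and so erodes the power. If that held, 10%, 20% or 30% inactive in both arms would turn 57% against 28.5% into 61.3% against 35.7%, 65.6% against 42.8% or 69.9% against 49.9% (for example 0.10 + 0.90 × 0.57 = 0.613). Power with 44 completers per arm, by the pooled formula, would fall from 78% to 68%, 58% or 48%. The documents do not support this reading. They give no item scoring, and the 26.55 cut-off appears only in the sample-size paragraph, while Aim 1 compares mean scores.

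**Conclusion.** The concern holds for the dyspareunia item and should be fixed. As the plan is written, a woman whose most bothersome symptom is dyspareunia and who has not attempted intercourse can be recorded as improved by up to 3 points, the full range of the scale. The effect on Aim 2 is noise and dilution if abstention is equal between arms, and bias if it is not. The 0.05 to 0.40 range rests on assumed abstention and scores; with no inactivity rate in the documents, the actual size is unknown.

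For the FSFI, dependence on activity is plausible from domains such as lubrication, orgasm and pain, but it remains an assumption until the scoring rule and recall period are stated. A reader might also infer that enrolment or the primary analysis should be limited to active women. The documents do not support that: women who want to resume are a legitimate target population, restriction to women active at baseline brings no real gain in precision on the illustrative inputs, and it would leave women who stop later in the FSFI comparison.

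**What to change.** 1. Record whether sexual activity occurred in the recall period, at baseline and at 12 weeks (and at four weeks if the symptom rating named in Aim 2 is collected then). Take the baseline answer before the allocation envelope is opened; the Study Plan's alternative route allows baseline questionnaires by telephone after allocation.
2. Add a not-attempted response to the dyspareunia item, split into because of pain and other reason, and do not score it as 0. In the mean-change analysis, give because of pain a change of zero (baseline score carried forward). Treat other reason as missing under the trial's missing-data method, which the plan must state because it describes none. Add a sensitivity analysis to both choices. A woman giving this response at baseline has no score to carry forward, so her change is also missing; show these counts by arm.
3. Keep all randomised women as the primary FSFI analysis. State the FSFI scoring rule and recall period, add a supporting analysis in women active at baseline, and report by arm how many resumed and how many stopped.

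The cost is two extra tick boxes, a little more analysis, and some Aim 2 values treated as missing. Table 1 and the sample size need no change on this account.

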[name]

Ospemifene versus Conjugated Estrogens in the Treatment of Postmenopausal Sexual Dysfunction

[name]

Female Pelvic Medicine and Reconstructive Surgery, Fellow
Emory University

[name], PhD

Female Pelvic Medicine and Reconstructive Surgery, Division Director & Fellowship Director
Associate Professor
Emory University Hospital, Chief of Service

[name], MPH, NCMP

Department of Obstetrics & Gynecology, Associate Professor
Menopause Clinic, Director
Emory University

Abstract & Relevance

57% of postmenopausal women suffer from female sexual dysfunction (FSD). Vulvovaginal atrophy (VVA) is a condition that impacts up to 60% of the growing postmenopausal female population, and the most common symptom is dyspareunia. Women with FSD are 3.84 times as likely to also have VVA. Vaginal estrogen is the most common treatment for VVA, but it only marginally improves overall sexual function, and many women and clinicians avoid using it because of the risks of exogenous estrogen use during menopause. Ospemifene is a SERM that is FDA-approved for dyspareunia related to VVA, and has shown superb improvements in overall sexual health. This oral medication, taken daily, improves vaginal health, and has demonstrated protective activity in the breast and bone tissues. It also has not demonstrated any carcinogenic activity in the endometrium or liver. This study hopes to determine if ospemifene is superior to conjugated estrogens in improving sexual function and vaginal atrophy symptoms. 104 women will be randomized to receive 12 weeks of 60mg oral ospemifene, taken daily, or 12 weeks of 0.5mg vaginal conjugated estrogens, which is placed vaginally twice per week. The improvements in sexual health and VVA symptom severity will be compared in each group. This study will help determine if ospemifene is a better treatment medication than conjugated estrogens. The implications of this study may provide an attractive alternative to the many women who continue to suffer from sexual dysfunction and VVA because of concerns surrounding the use of exogenous hormones.

Introduction

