In essence, Ospemifene seems to be a possible wonder drug for menopausal women. While it's primary use is for VVA-associated dyspareunia, there is consistent evidence of protective activity in bone and breast tissue, while showing no evidence of carcinogenic potential in the endometrium, breast, or liver. Similar to vaginal estrogen, ospemifene has not been studied longer than 12 months to determine long term risks of the medication [6]. Appendix 1 shows a summary of adverse events in various safety studies for vaginal estrogen and ospemifene. Research is

promising that Ospemifene may prove to be a safer and more beneficial choice for all postmenopausal women, regardless of their history of breast or endometrial cancer.

Innovation

Several studies have published data regarding the unique behavior of ospemifene in postmenopausal women. Nonetheless, vaginal estrogen is still seen as the gold standard for the treatment of VVA, regardless of the woman's most bothersome symptom. To our knowledge, for the first time, this study will directly compare the efficacy of vaginal conjugated estrogens and ospemifene in improving sexual function in postmenopausal women who have vulvovaginal atrophy. By also directly comparing symptom improvement with VVA treatment, this study hopes to answer the question of whether or not clinicians should shift towards ospemifene as a first line treatment for sexual dysfunction in postmenopausal women with VVA.

Approach

Overview

This study will be a prospective, randomized study that will compare efficacy and safety of ospemifene and vaginal estrogen. Because of the route of administration for each drug, it is not possible to blind the participants or clinicians to the treatment. However, we will be collecting objective data that cannot be misinterpreted by those collecting and analyzing the data. We hope to effectively inform clinicians who treat postmenopausal women that suffer from VVA about the efficacy of ospemifene as it compares to vaginal conjugated estrogens cream. As a specialty with a high population of patients who complain of VVA, we are very familiar with this patient population, as well as the use of vaginal estrogen in their treatment. This puts this research team in an ideal position to properly execute the study and interpret the findings.

Patient Groups

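### Entry does not require the FSFI-defined dysfunction on which the trial is sized, and Aim 1 neither adjusts for baseline FSFI nor secures it before allocation

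*Combined protocol and SAP*

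**What the plan says.** The title is "Ospemifene versus Conjugated Estrogens in the Treatment of Postmenopausal Sexual Dysfunction". The Innovation section says the trial should help settle "whether or not clinicians should shift towards ospemifene as a first line treatment for sexual dysfunction in postmenopausal women with VVA".

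The Sample Size Analysis takes FSD as "defined as having an FSFI score of 26.55 or less" and continues: "With an FSD prevalence of 57%, we determine a 50% reduction in the prevalence to be clinically significant". It then gives "Setting an alpha of 0.05, and a power of 0.80" and, after an allowance of at least 15% for dropout, "the sample size is set to 52 in each group".

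On symptoms, Table 1 (Inclusion Criteria) asks for "Dyspareunia as a vulvovaginal atrophy symptom". Neither Table 1 nor Table 2 sets an FSFI threshold or asks for a diagnosis of FSD. Under Patient Groups, the FSFI is completed after a woman has been enrolled, so it does not act as a screening test. Under Study Plan, an alternative route for busy clinics has the woman consent and receive her assignment in person, then complete the questionnaires in a call later that day.

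Aim 1 compares the change in FSFI total and domain scores between the arms at 12 weeks, names a paired t-test, and does not adjust for baseline.

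**The concern.** The condition in the title and in the sizing is not a condition of entry. A woman with mild dyspareunia and an FSFI of 30 meets Table 1. By the definition used for sizing she has no dysfunction to resolve, and she has less room to improve than a woman who starts low. Baseline FSFI can therefore be expected to differ a good deal between women.

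Three things follow.

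- **Interpretation.** A result from all randomised women describes women with VVA dyspareunia, but the plan presents it as a comparison in sexual dysfunction. The stated null is that the drugs have similar efficacy, so a non-significant result in a mixed population could be misread as showing that the two drugs treat dysfunction equally well.
- **Precision.** Unadjusted change scores make poor use of a baseline measure that varies this much.
- **Bias.** The trial is open-label and the FSFI is self-reported. Where the baseline form follows the assignment, knowing the drug can colour the baseline answers, and those answers enter every change score with full weight.

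**Working it through.** **Inputs.** 104 women, 52 per arm; FSD 57%, halved to 28.5%; alpha 0.05 (taken as two-sided, since the plan does not say); power 0.80; dropout 15% (Sample Size Analysis). VVA in up to 60% of postmenopausal women, and women with FSD 3.84 times as likely to have VVA (Abstract). The Abstract and the Significance section give the 57% for postmenopausal women generally.

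**1. The plan's sample size.** Two proportions, unpooled variance:

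n = (0.57×0.43 + 0.285×0.715) × (1.96 + 0.84)² / 0.285² = 0.4489 × 7.85 / 0.0812 = 43.4, so 44 per arm; 44/0.85 = 51.8, so 52.

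This matches the plan. The 80% power therefore fits a comparison of FSD proportions, not of FSFI change.

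**2. Women who may start above 26.55.**

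- If 57% applied to those enrolled: 104 × 0.43 = 44.7, about 45 (43%).
- If 3.84 is an odds ratio, let q₁ and q₀ be FSD prevalence with and without VVA. Solving 0.6q₁ + 0.4q₀ = 0.57 with odds(q₁) = 3.84 × odds(q₀) gives q₁ = 0.699 and q₀ = 0.377. Then 104 × 0.301 = 31.3, about 31.
- If 3.84 is a risk ratio: P(VVA | no FSD) = 0.6 / (0.57×3.84 + 0.43) = 0.229; P(VVA | FSD) = 3.84 × 0.229 = 0.880; P(FSD | VVA) = 0.57 × 0.880 / 0.6 = 0.836. Then 104 × 0.164 = 17.1, about 17.

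The last two counts are for women with VVA. Every entrant must also have dyspareunia, which probably lowers them further. The plan gives no figure for that step.

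**3. Adjusting for baseline.** Assume the same SD σ at both times and correlation ρ between them. The variance per woman is 2σ²(1−ρ) for change and σ²(1−ρ²) for ANCOVA. The ratio, ANCOVA over change, is (1+ρ)/2, which is below 1 for any ρ below 1. The plan gives neither σ nor ρ, so the gain cannot be put in FSFI points.

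**4. The group at or below 26.55.** Its size would be 104 × 0.57 = 59, 104 × 0.70 = 73 or 104 × 0.836 = 87 women before dropout. With SD unchanged, the standard error of the arm difference grows by 1/√0.57 = 1.32, 1/√0.70 = 1.20 or 1/√0.836 = 1.09.

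**The case against.** The strongest reply is that eligibility already fits the hypotheses. Aim 1 is about women with dyspareunia and VVA, and the null hypothesis is about sexual function in women with VVA. The analysis is of FSFI scores, including the pain domain, not of resolution of FSD. Whether to restrict entry by FSFI is then a design preference. This stands, and it is why a cut-off is not asked for here.

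The Significance section also gives a wider definition of FSD that includes pain. On that reading dyspareunia may itself count, and every entrant could have the condition. This stands for that definition, but the sizing uses the FSFI cut-off, and pain alone need not bring a woman to 26.55. The two definitions are left unreconciled.

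The 57% may also be a 12-week rate. The sentence that introduces it concerns women using vaginal conjugated estrogens. If 57% and 28.5% are 12-week rates across everyone enrolled, women above the cut-off are already averaged in and the sizing is not diluted. The plan does not say which is meant.

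A reader might go further and infer that about 45 of the 104 women are expected to lack the condition. The documents do not support that: the 57% describes menopausal women in general, while every participant must have VVA dyspareunia. A reader might also infer that 80% power falls to Φ(2.80×0.57 − 1.96) = 36%. That assumes no difference between arms in any woman above 26.55, although such a woman still has pain that can improve. It also degrades an 80% that the plan never establishes for FSFI change, for which it gives no SD or effect size.

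**Conclusion.** The mismatch is real and its size is uncertain. The title, the first-line question and the sizing concern sexual dysfunction, and the sizing uses FSFI 26.55 or less, while entry neither requires nor screens for that score. The share starting above the cut-off is not stated. It is about 43% (45 of 104) at the upper end and about 17 to 31 of 104 on the protocol's own association, probably fewer with dyspareunia required.

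These figures assume VVA prevalence of 60% (the protocol says up to 60%), 3.84 read as either an odds ratio or a risk ratio, and entry criteria that do not lower FSD prevalence below the general figure. The criterion of interest in sexual activity could work against the last assumption, and the documents give nothing to quantify it.

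What needs correcting is the handling of baseline FSFI and the wording of the conclusion. Neither the choice of population nor the 52 per arm is shown to be wrong. No loss of power can be calculated for Aim 1 from what the plan provides.

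**What to change.** 1. Have every woman complete the baseline FSFI, and score it, before her envelope is opened. In the alternative route, the questionnaire must come before the assignment.
2. Replace the Aim 1 comparison of change with a between-group ANCOVA of 12-week FSFI adjusted for baseline FSFI. This also removes the paired t-test, which does not suit two independent arms.
3. Describe the all-women result as applying to women with VVA dyspareunia. Prespecify the group with baseline FSFI of 26.55 or less as a supportive analysis, and state that it has lower power (a standard error about 9% to 32% larger on the figures above).
4. State whether the 57% is a baseline prevalence or a 12-week comparator rate, and reconcile the two definitions of FSD.

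Items 2 to 4 use data already planned and cost only text. Item 1 costs some convenience in busy clinics.

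An FSFI entry cut-off remains an option with a real price. Enrolling 104 would need about 183, 149 or 125 otherwise eligible women at 57%, 70% or 83.6% prevalence (104 divided by each). The sample size would have to be re-derived if 57% is a baseline prevalence. If it is a 12-week rate it would need fresh justification, because every woman would then begin with dysfunction.

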Once a qualifying subject is identified, she will be randomized into a treatment group. The participant will be randomized to receive either a vaginal conjugated estrogens prescription or an ospemifene prescription. A computerized randomization program will be used to perform block randomization in random blocks of 4 and 10. Allocations envelopes containing the assignment will be used for the study. They will be sealed opaque envelopes with aluminum foil inside. They will also contain carbon-copy paper. The treatment number will be printed on the envelope. Once the participant has signed the informed consent form, her name will be printed on the envelope, which will transfer over to the carbon-copy paper, and the envelope will be opened.

Study Plan

The patient will be informed of her assigned medication, and she will receive a medication coupon to help offset the cost of the medication. Each medication is FDA-approved for long-term use of at least 52 weeks. For this study, a 12-week prescription for the medication will be sent electron-

[figure not shown]
ically to the pharmacy of her choice. Treatment with estrogen will consist of 0.5 gram of conjugated estrogens placed vaginally for 12 weeks. Treatment with ospemifene will consist of a 60mg tablet that will be taken at the same time daily for 12 weeks.

The patient will receive an intake packet that includes the following information:

1. Copy of signed informed consent form
2. Important contacts and instructions for emergency/adverse events
3. Allocation card
4. Medication's FDA packet insert
5. Instructions on dosing
6. 12-week date to repeat questionnaires

She will be called the following day to confirm her start date of the medication. They will return at 12 weeks and complete the same FSFI and Likert Scale questionnaires regarding sexual function and VVA symptoms. The questionnaires may also be completed over the phone with the investigator.

Alternatively, if time during clinic is limited, the patient can be consented and allocated to a medication in person, by a co-investigator. She will be called by a co-investigator on the same day to complete the enrollment and questionnaires. Below is a summary of the study plan.

Sample Size Analysis

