Anticipated Results and Interpretation: Similar to objective findings, prior studies have shown significant improvement in VVA symptoms in patients using ospemifene or vaginal estrogen. We anticipate that the improvements seen with ospemifene will be comparable to those seen with vaginal estrogen.

Potential Pitfalls, Alternative Approaches, and Future Directions: The Likert scale is commonly used to assess symptom improvement in VVA treatment studies. We do not anticipate any pitfalls in this specific aim.

Safety Monitoring

Participants in the study will be provided with contact information to be used in the case of an adverse event related to the medication. For emergencies, they will be instructed to dial 911 and/or seek immediate medical attention. They will be instructed to contact the study team at [contact], to inform the team about any adverse event that may be related to the medication.

All reports of injury will be logged in one password-protected electronic file, by members of the study team. Patient data, including adverse events will be reviewed every two weeks by the [name] and [name]. Appendix 1 shows adverse events that have been documented during prior clinical trials of the two medications. This data will be used to determine whether the study will be discontinued due to occurrence or frequency of any given adverse event.

Individual Stopping Rules

Any event that involves new onset of vaginal bleeding, cardiovascular event, venous thromboembolism, or new diagnosis of cancer, will require the individual to discontinue the medication and withdraw from the study.

Timeline

Item	Start	Complete/Submit
IRB application	Started	November 1, 2016
Grant/Funding applications	Started	February 2017
Subject recruitment	November 1, 2016	August 1, 2017
Data Analysis	March 1, 2017	August 30, 2017
Thesis/Report	November 15, 2017	December 1, 2017

Required Resources & Budget

Resource	Estimated Cost
Personnel	
Consent forms, severity scale, questionnaire, other paper documents	
Counseling office	

\$10 gift cards for return visit, 104 subjects	\$1040.00
--	-----------

References

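### Table 2 excludes past arterial and cardiac disease but does not clearly exclude a resolved past DVT or PE in a woman now off anticoagulants

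*Combined protocol and SAP*

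**What the plan says.** Eligibility is set by Tables 1 and 2 in the Patient Groups section: "Once the exclusion criteria have been applied (Table 2), the qualifying subjects will be enrolled in the study". The Randomization and Allocation Concealment section follows on from this: "Once a qualifying subject is identified, she will be randomized into a treatment group". No further medical-history screen is described.

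Three lines of Table 2 could bear on a past venous clot:

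- the arterial and cardiac line, "History of CVA, MI or heart disease, uncontrolled HTN over 160/100";
- the clotting line, "Hypercoagulable state, or currently on anticoagulant therapy";
- the general-illness line, "Serious disease or chronic condition that may prevent completion of study, BMI over 40".

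No line names DVT, PE, VTE or past thrombosis. The Individual Stopping Rules list the events after which a participant must stop the drug and leave the study: "Any event that involves new onset of vaginal bleeding, cardiovascular event, venous thromboembolism, or new diagnosis of cancer". VTE appears there as its own item, beside cardiovascular events. Appendix 1 also has a row that combines cardiovascular events with VTE.

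**The concern.** The table treats arterial and venous disease differently. A past arterial or cardiac event excludes a woman by its history alone. For venous disease the table asks about a clotting tendency or present anticoagulant use, and a past event is not mentioned. The protocol gives no reason for the difference.

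What is at stake is participant safety and who may be randomised. The plan keeps out women with a clotting tendency and withdraws any woman who has a VTE on study, so it plainly regards VTE as a relevant harm. Much of the protection has to come from screening. After allocation, the Study Plan schedules a next-day call and a 12-week assessment that may be done by phone. Under Safety Monitoring, adverse events reach the team through participants making contact. The sample size and the planned analyses are not affected.

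**Working it through.** No arithmetic applies. The check is to take a test case through the eligibility text.

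**Test case.** A postmenopausal woman meets every line of Table 1. Some years ago she had a provoked DVT or PE. It was treated, has resolved, and she no longer takes an anticoagulant.

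**Step 1: the arterial and cardiac line.** "History of CVA, MI or heart disease, uncontrolled HTN over 160/100" names stroke, heart attack, heart disease and uncontrolled hypertension. A DVT is none of these, and a resolved PE is not obviously heart disease. The stopping rules also list VTE separately from cardiovascular events, so the plan's own vocabulary gives no ground for reading venous events into this line.

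**Step 2: the clotting line.** This has two halves.

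- The anticoagulant half is limited to present use. She is off treatment, so it does not apply.
- The hypercoagulable half carries no time limit and is not defined. It describes a condition, not a past event. An investigator could count any past clot as evidence of the condition. Another could regard a provoked, resolved clot as no such evidence. The text decides neither way.

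**Step 3: the general-illness line.** "Serious disease or chronic condition that may prevent completion of study, BMI over 40" turns on whether a condition threatens completion of the study. A resolved clot need not. The BMI limit would catch her only by coincidence.

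**Step 4: the remaining lines.** "Pelvic surgery within the last 12 months" would catch a clot provoked by recent pelvic surgery, but only through the surgery and only for a year. "Genital bleeding of unknown cause" and the lines on tumours, vaginal infection and sex-hormone use do not concern clotting.

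**Step 5: safeguards outside Table 2.** The stopping rule acts on events after enrolment, so it does not screen for past ones. The package insert is given in the intake packet together with the allocation card, that is, after randomisation. Its content is not in the documents.

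**Result.** On a literal reading she can be randomised to either arm. On a broad reading of the undefined term she is excluded. Her eligibility depends on which investigator screens her.

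**Size.** The only related figures are in Appendix 1: 0.3% for ospemifene at 12 weeks and 0% at 52 weeks. They pool cardiovascular events with VTE and do not describe women with a prior clot, and that row shows no figure for conjugated estrogens. The documents give no prevalence of past VTE. No expected count can responsibly be derived from this.

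**The case against.** The strongest reply is that the plan already has a clotting exclusion and the gap depends on one reading of it. The word limiting the line to present use attaches only to anticoagulants. Recruitment takes place in specialist clinics, after a plan to treat atrophy has been made, and the investigators approach the patients themselves, so the most permissive reading is less likely in practice. This stands in part. It narrows the affected group to women with a resolved clot, off treatment, whom the screener does not judge hypercoagulable. It does not settle how they should be handled.

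A reader might infer that Table 2 has nothing at all on VTE. It does: the clotting line is a partial counterpart, just as "Genital bleeding of unknown cause" is a partial counterpart to new vaginal bleeding.

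A reader might also infer that the stopping rules oblige the plan to exclude on VTE history, so that the two sections contradict each other. They do not. A stopping event need not be a history exclusion, and the plan does not treat it so elsewhere: any new cancer ends participation, but the tumour exclusions cover only breast and hormone-dependent tumours.

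Finally, it is tempting to say that either drug is known to be unsafe after a past clot. The documents hold no data on such women and do not reproduce the labelling, so that claim is not made here. The objection that the harm is unquantified stands in full.

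**Conclusion.** The point holds as a gap in eligibility wording. Table 2 covers VTE risk only in part and, read literally, admits a woman with a resolved DVT or PE who is off anticoagulants, while past arterial and cardiac disease is excluded by name. Two assumptions support this: that eligibility is decided on Tables 1 and 2 as written, and that at least some screeners would not read a hypercoagulable state to include every past clot. The number of women affected and their excess risk cannot be estimated from the documents. Because the change would alter who may be randomised and serves safety at very little cost, it should be made. Confidence is medium, since the clotting line can reasonably be read more broadly.

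**What to change.** Add a criterion to Table 2, beside the existing clotting line: history of or current venous thromboembolism (DVT or PE). Apply it with the other exclusions before randomisation, as the enrolment steps already provide. If the investigators already intend to exclude these women, the line records that intent and makes screening uniform; if they do not, it closes the gap.

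The cost is one line of text and one more screening question. The downside is that probably a few women become ineligible; how many cannot be estimated from the documents. The enrolment procedure, stopping rules, planned sample size and analyses need no change.
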